## **8.8 Safety Oversight**

### **8.8.1 Data Safety and Monitoring**

The Principle Investigator will ensure overall safety of the subjects in the trial on a daily basis and will be responsible for all reporting. The site PIs will be responsible for managing safety at their sites in coordination with the PI. The study statistician will be responsible for running quarterly reports on data safety, consistency and outcomes and reviewing them with the study PI. A DSMB will act in an advisory capacity to the Primary IC Director in regards to the study.

### **8.8.2 Frequency and Reporting**

As noted in [section 8.4](#), all AE and SAE will be reported directly to the site PI and then study PI. All events will be reported within 24 hours to the DSMB and the IRB at both the study site and the primary IRB (NYU). The DSMB will then discuss whether and how to convene. Outside of SAE, the DSMB will meet at least prior to onset of the trial and every 6 months at a minimum. Safety reports will be sent twice yearly including analysis of study progress and data and safety issues. These reports will include descriptive analyses of participant demographic data, interim analyses of primary and secondary outcomes, as well as any adverse or serious adverse events, and quality improvement program fidelity. Individuals who withdraw from the trial will be examined in sensitivity analyses, however will be replaced with completed cases for the purposes of the trial. There are no cases where the quality improvement program will be discontinued but follow-up will still occur unless an individual withdraws from the study due to an AE or SAE, in which case we will ensure safety of the individual/dyad and referral to existing resources.

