### **5.6 Total Number of Participants and Sites**

Recruitment will end when approximately 345 dyads (345 PWD and 345 caregivers) are enrolled. It is expected that approximately 345 dyads will be enrolled in order to produce 300 evaluable dyads.

Sample at VNAHG Site: 207 dyads (207 PWD, 207 caregivers) enrolled, with expectation of 180 complete dyad cases (180 PWD, 180 caregivers).

Sample at University of Utah Site: 86 dyads enrolled (86 PWD, 86 caregivers) with expectation of 75 complete dyad cases (75 PWD, 75 caregivers).

Sample at University of Miami Site: 52 dyads enrolled (52 PWD, 52 caregivers) with expectation of 45 complete dyad cases (45 PWD, 45 caregivers).

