#### **5.7.2 Handling of Participant Withdrawals or Termination**

Given the minimal risk nature of this study, individuals who chose to withdraw from the study will not continue to be followed in any form. We have factored in a 15% study non-completion rate and anticipate recruiting 345 dyads to meet the 300 dyads required study participants. Subjects will not be disenrolled based on data related issues. If subjects are unable to attend intermediate visits (Visit 2 and/or 3), those visits will be counted as missed. If the caregiver does not complete visit four, both subjects will be terminated from the study.

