## 10.3 Analysis Datasets

PWD, caregivers, and clinicians will each have a separate data set. Additionally, a data set with combined will be created to examine the interaction between PWD-caregiver dyad interactions and interactions between outcomes and quality improvement program fidelity. Separate SAE and AE data sets will be maintained for caregivers and PWDs.

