## 10.4 Description of Statistical Methods

### 10.4.1 General Approach

Data Analysis will be performed using SAS 9.4. We will perform statistical tests to examine baseline differences between the quality improvement program and control groups. We will then perform unadjusted comparison of both primary outcomes (patient and caregiver quality of life, emergency room visits) and secondary outcomes (pain, BPSD, delirium, caregiver depression burden, and burnout, hospital and emergency room admissions) between groups. We will focus on the endpoint measure for quality of life, and 30 and 60-day outcomes for emergency room utilization. For primary and secondary outcomes, we will perform a time trend analysis using a mixed effects linear model (PROC MCM). Mixed effects regression is used to analyze longitudinal data with repeated measures accounting for intra-individual and group clustering. We intend to use multivariate mixed effects regression modeling as opposed to traditional linear modeling or ANOVA in order to control for unobservable confounding variables that are constant over time but differ across PWD and/or caregivers. For both primary and secondary outcomes, we will then repeat the above analyses adjusting for baseline variables as covariates for a more efficient measurement of the effects of the quality improvement program. We will also perform correlation analyses to explore the relationship between pain and BPSD, and PWD and caregiver QOL through plotting scores over time and then if a significant correlation is present through adding to our mixed effect model. For utilization data, we will perform logistic regression to examine whether the patient is more or less likely to have a hospitalization or ER visit compared when receiving the quality improvement program at 30 and 60 days. We will then perform a Poisson Count Regression to compare the total number of hospitalizations and ER visits at each timepoint. In these models we will utilize a random effect to measure for clustering.

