## 10.5 Sample Size

Power analyses were conducted using Optimal Design software. Given that this study is randomized at the cluster level, we must control for intra-class correlation, and have therefore calculated all power with an intra-class coefficient of .05, which is more conservative than the most recent clustered palliative care study and aligns well with prior community-based cluster trials. The Quality of Life in Alzheimer's Disease as the primary outcome measure in aim 1 has an average score of 33.1, standard deviation of 5.9. A .5 standard deviation difference in this measure would be clinically meaningful. Therefore, in a 2-sample comparison with a power of .80, an alpha of .05 and covariates that account for a cumulative 15% of the variance in outcome would require 15 dyads per cluster, and 20 clusters (10 per arm) at 60 days to detect a medium effect ( $\delta = .45$ ). For mixed effects linear models, the projected sample size will also allow us to detect a medium linear treatment effect ( $\delta = .45$ ) between groups in unadjusted analyses (assuming 15 dyads per cluster, 20 clusters, 4 observations, and an ICC = .05). Although there are no closed-form equations for calculating the power of linear models that include covariates, any non-zero correlation between covariates and the outcome will reduce the unexplained (error) variance thus increasing the statistical power of our tests, and reducing the minimum detectable effect size. As such, the detectable effect size estimated for the unadjusted analyses can be considered an upper bound estimate for the effect size detectable in adjusted analyses. **We will recruit until we have reached 15 completed cases in each cluster (N=300).** Conservatively anticipating a 15% dropout over the 60 days requires a **total recruitment goal of 345 dyads**. As almost 20,000 patients are seen each year in the three HHC agencies in this study, approximately 30% with ADRD, we do not expect any difficulty recruiting this sample, even with an unanticipatedly high rate of dyads declining to participate.

In addition, for fidelity monitoring, as discussed in section [6.1.6.1](#), we will consent **300 clinicians** at the participating HHC agencies on usual care and quality improvement care teams to complete fidelity monitor by performing the DSKA survey. These clinicians are not study subjects but will be consented as they are

CONFIDENTIAL

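### No primary analysis population is defined, and the rules on replacement, termination and recruitment read most naturally as a completer-only analysis

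*Combined protocol and SAP*

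**What the plan says.** - **Withdrawals (8.8.2).** Individuals who withdraw "will be examined in sensitivity analyses, however will be replaced with completed cases for the purposes of the trial".
- **Follow-up and termination (5.7.2).** It says that "individuals who chose to withdraw from the study will not continue to be followed in any form" and that "If the caregiver does not complete visit four, both subjects will be terminated from the study". Section 5.4 repeats the visit 4 rule. Section 5.7.2 also says "Subjects will not be disenrolled based on data related issues", and a missed visit 2 or 3 is simply recorded as missed.
- **Target number.** Section 5.6: "It is expected that approximately 345 dyads will be enrolled in order to produce 300 evaluable dyads". It does not define evaluable. Section 10.5 also counts completers: "We will recruit until we have reached 15 completed cases in each cluster (N=300").
- **Analysis sets (10.3).** "PWD, caregivers, and clinicians will each have a separate data set". The section goes on to a combined file and to AE and SAE files. It does not say which enrolled dyads enter the primary comparison.
- **Models (10.4.1).** "For primary and secondary outcomes, we will perform a time trend analysis using a mixed effects linear model", with logistic and Poisson regression for utilization. No missing-data assumption or rule for partial follow-up is given.
- **Loss (10.4.3).** Retained subjects are compared with those withdrawn or terminated, but the treatment effect is not re-estimated.
- **SAP (10.1).** None will be written.

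**The concern.** Taken together, these rules take a dyad without a completed visit 4 out of the trial, replace it with one that has completed, and send at least those who withdraw to sensitivity analyses. Nothing in sections 10.1 to 10.4 puts them back. An analyst following the text could reasonably drop enrolled dyads from the randomised comparison. Another, reading replacement as top-up, could keep them.

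Two things are at stake. First, collected data would be discarded. Visit 3 records utilization, and section 3.1 makes ER visits and admissions at 30 days part of the Aim 3 primary outcome. A dyad lost between visits 3 and 4 has that 30-day outcome. Pain and BPSD values at days 15 and 30 would go too. Second, loss could depend on the outcome. Section 5.4 names re-hospitalization among the greatest threats to retention, and hospital admission is an Aim 3 primary outcome.

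The choice should be fixed in advance. The statistician randomises the teams and the PI relays the allocation (4.1), and the two review quarterly outcome reports together (8.8.1).

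**Working it through.** **1. Dyads affected.** The plan's figure: 300 × 1.15 = 345 recruited for 300 completed. So 345 − 300 = 45 dyads, or 45/345 = 13.0%, lie outside the completed cases. At a true 15% loss from 345 it would be 0.15 × 345 ≈ 52.

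**2. Admission comparison among completers.** Inputs:
- Loss of 15% per arm, from 5.7.2 and 10.5, taken as equal in the two arms (assumption).
- Admission risk p of 20% (assumption), or 63.8%. Section 4.2.1 equates a 10% reduction with 63.8 fewer admissions per 1000. So 63.8/0.10 = 638 per 1000, read here as a risk (assumption).
- Admitted dyads lost r times as often as others (assumption; the documents give no value).

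Formulas: d0 = 0.15/(p·r + 1 − p) is the loss among those not admitted, and d1 = r·d0 is the loss among those admitted. Since total loss is 15%, completer risk = p(1 − d1)/0.85.

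Worked case, p = 0.20:
- r = 2: d0 = 0.15/1.2 = 0.125, d1 = 0.25, completer risk = 0.20 × 0.75/0.85 = 0.1765.
- r = 3: d0 = 0.15/1.4 = 0.1071, d1 = 0.3214, completer risk = 0.20 × 0.6786/0.85 = 0.1597.
- With no true effect, RR = 0.1597/0.1765 = 0.905.

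| r in DSM-H vs control | Null RR, p = 20% | Null RR, p = 63.8% |
|---|---|---|
| 3 vs 2 | 0.1597/0.1765 = 0.905 | 0.6022/0.6131 = 0.982 |
| 2 vs 3 (reversed) | 1.105 | 1.018 |
| 1.5 vs 1.25 | 0.1872/0.1933 = 0.968 | 0.6225/0.6292 = 0.989 |

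These are scenarios, not limits. With r = 4 in DSM-H and r = 1 in control at 20% risk, the ratio is 0.1471/0.200 = 0.735.

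**3. Same loss pattern in both arms.** The completer odds are p(1 − d1)/[(1 − p)(1 − d0)]. If d0 and d1 are the same in both arms, the selection factor cancels and the odds ratio is unchanged. A true RR of 0.90 reads 0.897 (p = 0.20, r = 2) to 0.890 (p = 0.638, r = 4).

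**4. QOL-AD.** Bias = loss × gap in one arm minus loss × gap in the other, where the gap is how much worse lost dyads are (assumed).
- Equal 15% loss, gaps of 0.5 and 0.25 SD: 0.15 × 0.5 − 0.15 × 0.25 = 0.0375 SD, or 0.22 points at the SD of 5.9 in section 10.5.
- Loss of 10% versus 20%, same gap of 0.25 to 1.0 SD: 0.10 × gap = 0.025 to 0.10 SD, or 0.15 to 0.59 points.

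The comparator is the detectable effect of 0.45 SD (2.66 points). Table 2 collects both QOL primaries only at days 0 and 60. A dyad without visit 4 therefore supplies a baseline value at most, and adds almost nothing to the arm effect beyond a baseline-adjusted completer model. That adjustment removes most of the part of the bias that works through baseline QOL.

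**The case against.** **The plan does not state a completer-only rule.** This is correct. The word in 8.8.2 may mean recruitment top-up, which fits 5.7.2's link between 345 recruited and 300 required. The sentence sits in a section on safety reporting and speaks of withdrawals, not of dyads terminated for missing visit 4. A reader might infer that completer-only analysis is mandated; the documents do not go that far. What stands is that no other population is named, so the text supports both readings.

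**Safeguards weaken the link from admission to loss.** This also stands in part. Section 5.4 provides phone interviews at all time points, does not require the pair to attend together, and ties termination to the caregiver as respondent. A hospitalized PWD does not by itself mean a missed visit 4. Section 8.1 lists hospitalization among the monitored events. Section 7.2.7 asks about SAEs at withdrawal and reviews the agency record when contact is lost. Section 8.3 records SAEs until 30 days after last participation. These reduce the risk, but no section feeds SAE data into the Aim 3 analysis.

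**A mixed model already handles partial data.** If fitted by likelihood it can, under missing at random, but 10.4.1 states neither that assumption nor who enters the model. For the QOL primaries it gains almost nothing, as shown above.

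**A 10% shift could manufacture a positive Aim 3 result.** A reader might infer this, because 4.2.1 calls a 10% reduction meaningful. The 0.905 figure is one assumed scenario at one assumed risk. At the plan's own rate the same scenario shifts the ratio by about 2%, and the documents do not support any particular r.

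**Conclusion.** The point holds as an undefined primary analysis population whose surrounding rules lean towards completers. About 45 of 345 dyads (13%), and data already collected on some of them, are at stake. Bias is possible on admissions only if loss is tied to admission differently by arm. Its direction is unknown, and equal drop-out totals would not reveal it. Under the assumed scenarios, a null admission RR reads between about 0.905 and 0.99, or the reciprocals. Bias on QOL-AD, the powered outcome, is small. The sample size is not in question. The omission is certain and the bias only possible, so this should be fixed before outcome data are analysed; it does not invalidate the design.

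**What to change.** 1. **Section 10.3:** define the primary analysis set as all enrolled dyads, by their care team's assigned arm, using all data collected before loss or withdrawal, including day-30 utilization.
2. **Section 8.8.2:** state that top-up recruitment is allowed and that replaced dyads stay in the analysis.
3. **Sections 5.4 and 5.7.2:** record a missed visit 4 as missing follow-up, not termination, while respecting a choice to withdraw.
4. **Section 10.4.1:** state the missing-at-random assumption; make a baseline-adjusted or likelihood-based QOL model primary; use log(days observed) as offset in the Poisson model, with utilization counted to the PWD's date of death.
5. **Section 10.4.3:** keep the completer analysis as a sensitivity analysis, and report loss and deaths by arm and reason.

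Multiple imputation for the logistic models, agency-record data for lost dyads and a missing-not-at-random analysis are optional.

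Cost: a protocol amendment to wording and slightly more analysis work. The downside is reliance on a missing-data assumption, which would at least be stated.

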### **8.8.3 Data Safety and Monitoring Board**

#### **8.8.3.1.1 DSMB Composition**

The investigators will develop with the IC a 3-member independent DSMB. The composition will include a chair who has experience performing Phase III behavioral clinical trials in dementia, a biostatistician, and an independent clinician-researcher with experience in home-based care of older adults. All members will

CONFIDENTIAL

This material is the property of the NYU School of Medicine and Langone Medical Center. Do not disclose or use except as authorized in writing by the study sponsor

have no personal or professional conflict of interest in the study, a current affiliation with any of the study sites, has not served as an author or co-author on a grant or manuscript together with the PI or site PIs within the past 3 years.

#### **8.8.3.1.2 DSMB Responsibilities and Powers**

The principle responsibility of the DSMB is to protect the safety of study participant. The DSMB will initially meet to evaluate the protocol to ensure minimization of risk prior to initiation and recommend when subject recruitment can be initiated. The DSMB will then meet and monitor primary and secondary outcome data, SAEs and AEs, performance data by site, and recruitment data by site, as well as other safety issues or risks to the PWD, caregiver, or dyad through bi-annual meetings, or if needed more frequently via conference call or webex. The DSMB will have the power to recommend halting of the trial to the IC and PI should it find any of these factors cause safety issues, serious adverse events or outcomes, or significantly better outcomes. It also has the power to report directly to the IC and the PI on its findings or any issues with the conduct of the study or enrollment, sample size, or data collection issues. The quality improvement program will be discontinued or temporarily halted if the IC closes the trial or DSMB recommends discontinuing or halting the trial based on determining the study's subjects (care recipient and care giver) safety is compromised or at risk. ([see section 8.7](#)).

## **9 Clinical Monitoring**

Clinical site monitoring is conducted to ensure that the rights and well-being of human subjects are protected, that the reported trial data are accurate, complete, and verifiable, and that the conduct of the trial is in compliance with the currently approved protocol/amendment(s), with GCP, and with applicable regulatory requirement(s). As this is a minimal risk study, limited clinical monitoring will be performed by the study biostatistician in ensuring data entry verification and completeness and, the lead site principal investigator in ensuring appropriate and complete targeting of prospective subjects. As noted in fidelity measurement, we will also hold monthly meetings to ensure quality improvement program fidelity. Additionally, each research site will perform internal quality management of study conduct, data collection, documentation and completion.

## **10 Statistical Considerations**

### **10.1 Statistical and Analytical Plans (SAP)**

A formal SAP will not be completed for this study.

### **10.2 Statistical Hypotheses**

H1: PWD cared for by a HHC team utilizing the DSM-H will show reduced symptoms and improved ratings of pain, BPSD, and caregiver-rated QOL at the end of the first 60-day HHC certification period compared to the control (usual care) group.

H2: Informal caregivers of PWD cared for by a HHC team utilizing the DSM-H will show reduced ratings of burden, and depression, and improved functional health and well-being at the end of the first 60-day HHC certification period compared to the control (usual care) group.

H3: PWD cared for by a HHC team utilizing the DSM-H will show a reduction in emergency room visits and hospital admissions compared to the control (usual care) group, and a greater number of outpatient visits.

CONFIDENTIAL

This material is the property of the NYU School of Medicine and Langone Medical Center. Do not disclose or use except as authorized in writing by the study sponsor

Interventional Template Version: 28 APR 2017

## 10.3 Analysis Datasets

PWD, caregivers, and clinicians will each have a separate data set. Additionally, a data set with combined will be created to examine the interaction between PWD-caregiver dyad interactions and interactions between outcomes and quality improvement program fidelity. Separate SAE and AE data sets will be maintained for caregivers and PWDs.

## 10.4 Description of Statistical Methods

### 10.4.1 General Approach

Data Analysis will be performed using SAS 9.4. We will perform statistical tests to examine baseline differences between the quality improvement program and control groups. We will then perform unadjusted comparison of both primary outcomes (patient and caregiver quality of life, emergency room visits) and secondary outcomes (pain, BPSD, delirium, caregiver depression burden, and burnout, hospital and emergency room admissions) between groups. We will focus on the endpoint measure for quality of life, and 30 and 60-day outcomes for emergency room utilization. For primary and secondary outcomes, we will perform a time trend analysis using a mixed effects linear model (PROC MCM). Mixed effects regression is used to analyze longitudinal data with repeated measures accounting for intra-individual and group clustering. We intend to use multivariate mixed effects regression modeling as opposed to traditional linear modeling or ANOVA in order to control for unobservable confounding variables that are constant over time but differ across PWD and/or caregivers. For both primary and secondary outcomes, we will then repeat the above analyses adjusting for baseline variables as covariates for a more efficient measurement of the effects of the quality improvement program. We will also perform correlation analyses to explore the relationship between pain and BPSD, and PWD and caregiver QOL through plotting scores over time and then if a significant correlation is present through adding to our mixed effect model. For utilization data, we will perform logistic regression to examine whether the patient is more or less likely to have a hospitalization or ER visit compared when receiving the quality improvement program at 30 and 60 days. We will then perform a Poisson Count Regression to compare the total number of hospitalizations and ER visits at each timepoint. In these models we will utilize a random effect to measure for clustering.

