### 10.4.4 Baseline Descriptive Statistics

We will compare quality improvement program cohorts based on baseline demographic variables including age, sex, education, race, ethnicity, healthcare literacy, functional status, and comorbidities using descriptive statistics and t-tests.

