## 10.6 Measures to Minimize Bias

### 10.6.1 Enrollment/Randomization/Masking Procedures

As randomization is done at the cluster (care team) level, this will only be performed at the beginning of the trial. The study statistician will perform the randomization utilizing SAS 9.4 stratified by agency. The PI will relay to the home care agencies which teams will serve as quality improvement program teams or control teams. The study RAs, study project director, and site-PIs will all be blinded to the assignment. Teams will be randomized in strata by agency and geographic location to ensure like care teams are assigned to each condition. Subjects will be assigned through usual practice to the care team that serves the geographic area they live in. We will sequentially recruit individuals as they are referred from agencies following the very clear, straightforward method described above in section [5.4](#).

Clinicians will be enrolled sequentially if they are eligible and all study personnel with the exception of the lead site PI and study statistician will be blinded as to the assignment of the clinicians within a performance improvement or usual care team.

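### Baseline and interim t-tests, and the unadjusted outcome comparison in 10.4.1, carry no stated care-team term although care teams are randomised; if run as ordinary dyad-level tests, their error would be about 13% instead of 5%

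*Combined protocol and SAP*

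**What the plan says.** **Unit of randomisation.** Section 10.6.1: "As randomization is done at the cluster (care team) level, this will only be performed at the beginning of the trial". Sections 4.1 and 10.6.1 add stratification by agency and geographic location.

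**Sizing.** Section 10.5: "Given that this study is randomized at the cluster level, we must control for intra-class correlation". The authors "have therefore calculated all power with an intra-class coefficient of .05", and the design "would require 15 dyads per cluster, and 20 clusters (10 per arm) at 60 days to detect a medium effect".

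**Outcome comparisons.** Section 10.4.1 begins with tests of baseline differences and continues: "We will then perform unadjusted comparison of both primary outcomes (patient and caregiver quality of life, emergency room visits"), with the secondary outcomes in the same sentence. It then says: "We will focus on the endpoint measure for quality of life, and 30 and 60-day outcomes for emergency room utilization". No test is named and clustering is not mentioned. Next come the mixed model, described as handling within-person and group clustering, a covariate-adjusted repeat, and logistic and Poisson models with a random effect for clustering. The Protocol Summary describes the same three kinds of model and gives random effects to the utilization models.

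**Named simple tests.** Section 10.4.4 compares the arms on age, sex, education, race, ethnicity, "healthcare literacy, functional status, and comorbidities using descriptive statistics and t-tests". Section 10.4.2 plans two-sided t-tests at 0.05 for the interim safety analyses, presented unblinded to the DSMB. Neither mentions care team.

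**No later document.** Section 10.1 says that no formal SAP will be written, so section 10 is the whole analysis plan.

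**The concern.** Dyads served by the same team share clinicians and an area, so their outcomes are correlated. A test that treats 300 dyads as independent understates the standard error of the arm difference and rejects a true null too often.

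The plan recognises this in the sample size and in its regression models, but not in its simpler comparisons. An analyst who works from section 10 alone must choose a test for the unadjusted comparison, and the only simple arm tests that the section names for dyad data are ordinary t-tests.

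Three results are exposed:
- **Unadjusted outcomes.** This is the first efficacy result produced for each primary and secondary outcome. Section 10.4.1 puts its focus on endpoint QOL, no analysis is labelled confirmatory, and 10.4.7 marks multiplicity as not applicable.
- **Interim.** The DSMB would see p-values that are too small.
- **Baseline.** Dyads are recruited after teams are randomised, so the baseline table is the main check on whether the arms recruited alike. Tests that ignore team can report differences between areas as imbalance between arms.

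**Working it through.** **Inputs.** From 10.5: m = 15 completed dyads per team, 20 teams (10 per arm), ICC ρ = .05, alpha .05, power .80, δ = .45. Two-sided testing is stated only for the interim tests; it is assumed here for the others.

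**1. Reproduce the plan's figure.** For J = 20 teams, λ = J·δ² / (4·(ρ + (1−ρ)/m)), with a noncentral F on 1 and J−2 = 18 df.
- λ = 20 × .2025 / (4 × (.05 + .95/15)) = 4.05 / .4533 = 8.93.
- Power is 80.7%, and the effect detectable at 80% power is 0.446. The stated .80 and .45 therefore reproduce, as a *clustered* test without covariates.
- Section 10.5 describes this calculation as made "in a 2-sample comparison with a power of .80, an alpha of .05 and covariates that account for a cumulative 15% of the variance". With R² = .15 at team level, power is 83.3%; with R² = .15 at both levels, 86.5%. The printed figure matches the no-covariate case.

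**2. Error if care team is ignored.** Design effect DE = 1 + (m−1)ρ = 1 + 14 × .05 = 1.70. Two-sided error = 2·(1 − Φ(1.96/√DE)) = 2·(1 − Φ(1.503)) = 13.3%.

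| ICC | DE (m = 15) | Error |
|---|---|---|
| .01 | 1.14 | 6.6% |
| .02 | 1.28 | 8.3% |
| .05 (plan) | 1.70 | 13.3% |
| .10 | 2.40 | 20.6% |

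Only .05 comes from the plan; the other values are assumptions that show the range.

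**3. Checks by simulation at ICC .05 (100,000 null trials).** A dyad-level t-test rejects 13.5% of the time, and a t-test on the 20 team means 5.0%. A two-proportion test that ignores team, at an assumed 30% event rate, rejects 13.3%.

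**4. Baseline and interim.** Baseline tests would use all enrolled dyads, 345/20 = 17.25 per team. At ICC .05, DE = 1 + 16.25 × .05 = 1.81 and the error is 14.5%. This is illustrative, because 10.5 gives its ICC for outcome power and not for race, education or literacy. At an interim look, teams hold fewer dyads, so DE and the inflation per look are smaller than at the end.

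**5. Effect of stratification.** Suppose a share f of the between-team variance lies between strata and is balanced across arms. The variance ratio is then .95 + 15 × .05 × (1−f) = .95 + .75(1−f).
- f = 0: 1.70, error 13.3%.
- f = .5: 1.325, error 8.9%.
- f = 1: .95, error 4.4%.

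The plan gives no basis for f. Full balance within agency is not possible, because two agencies have odd numbers of teams (5 and 3, Protocol Summary).

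**6. Width of the interval.** √1.70 × t(.975, 18) / t(.975, 298) = 1.304 × 2.101 / 1.968 = 1.39.

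**The case against.** The strongest reply is that the outcome sentence in 10.4.1 is silent rather than wrong. Section 10.5 attaches the word *unadjusted* to mixed-effects models that already include ICC .05, and 10.4.1 later repeats its analyses with covariates, so *unadjusted* may mean only *without covariates*. The Protocol Summary lists only mixed, logistic and Poisson models. The 30- and 60-day utilization models already have a random effect. Stratification also removes some between-team variance.

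Most of this stands, and it limits the point:
- A reader might infer that the plan *prescribes* an independent-observations test of the primary outcomes at 13% error. It does not; no test is named there.
- A reader might infer that the two-sample comparison sized in 10.5 is this unadjusted one. That does not follow, because the calculation is described with covariates.
- A reader might infer that these are the only arm comparisons without a cluster term. They are not: the covariate-adjusted repeat of the simple comparison has none stated either.
- A reader might compound the error over the eight baseline variables. That would need independence between related variables and an ICC that the plan does not give.

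The reply does not close the gap. The 10.5 sentence on unadjusted models assumes four observations, while both QOL instruments are scheduled only at days 0 and 60 (7.2.2, 7.2.5, Table 2), so it does not define the endpoint QOL comparison. It also has no bearing on 10.4.4 and 10.4.2, where t-tests are named outright.

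**Conclusion.** The point holds as a gap in specification that should be closed. It is not a demonstrated error in the main models. The baseline and interim t-tests are named without a care-team term, and the unadjusted outcome comparison has neither test nor cluster term.

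If dyad-level tests are used, two-sided error for outcomes at 15 dyads per team is about 13% at the plan's ICC. That figure assumes equal team sizes, two-sided 5% testing and no gain from stratification, so at ICC .05 it is the upper end; 8.9% would apply if the strata absorbed half of the between-team variance. Baseline error rates cannot be fixed from the documents. The mixed, logistic and Poisson models already provide for clustering and are not challenged on this point.

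**What to change.** - **10.4.1:** Define *unadjusted* as without covariates. State that every unadjusted arm comparison of a primary or secondary outcome accounts for care team, either by a model with arm and a care-team random intercept tested on between-team degrees of freedom, or by an analysis of team means. Both should respect the randomisation strata. With 20 teams there are 18 degrees of freedom before strata are fitted; fitting the three agencies alone leaves 20 − 2 − 2 = 16. Carry the same rule into the covariate-adjusted repeat, and say which analysis is confirmatory.
- **Utilization:** State that the existing random-effect logistic and Poisson models, without covariates, are the unadjusted comparison. No new model is needed.
- **10.4.4, and the baseline tests in 10.4.1:** Report summaries by arm. If tests are kept, use ones that account for care team and that suit categorical variables such as sex, race and ethnicity.
- **10.4.2:** Apply the same rule to the interim t-tests.

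The cost is a few sentences, with no new data and no extra dyads. Unadjusted confidence intervals become up to about 39% wider at ICC .05 (on 18 df). The sample size in 10.5 already assumes that precision, so no planned power is lost.
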